5.4.6.11 Hospitalization or Prolonged Hospitalization

Any adverse event that results in hospitalization (i.e., in-patient admission to a hospital) or prolonged hospitalization should be documented and reported as a serious adverse event (per the definition of serious adverse event in Section 5.3.2), except as outlined below. The duration of hospitalization should also be noted on the eCRF.

The following hospitalization scenarios are not considered to be adverse events or serious adverse events:

- Hospitalization for respite care
- Planned hospitalization required by the protocol (e.g., for study drug administration or insertion of access device for study drug administration)
- Hospitalization for a preexisting condition, provided that all of the following criteria are met:

The hospitalization was planned prior to the study or was scheduled during the study when elective surgery became necessary because of the expected normal progression of the disease.

The patient has not suffered an adverse event.

The following hospitalization scenario is not considered to be a serious adverse event, but should be reported as an adverse event instead:

- Hospitalization that was necessary because of patient requirement for outpatient care outside of normal outpatient clinic operating hours

5.4.6.12 *Adverse Events Associated with an Overdose or Error in Drug Administration*

Study drug overdose is the accidental or intentional use of the drug in an amount higher than the dose being studied. An overdose or incorrect administration of study drug is not itself an adverse event, but it may result in an adverse event.

Any study drug overdose or incorrect administration of study drug should be noted on the Study Drug Administration eCRF.

All adverse events associated with an overdose or incorrect administration of study drug should be recorded on the Adverse Event eCRF. If the associated adverse event fulfills serious criteria, the event should be reported to the Sponsor immediately (i.e., no more than 24 hours after learning of the event; see Section 5.5.2).

5.4.6.13 **Patient-Reported Outcome Data**

Adverse event reports will not be derived from patient-reported outcome (PRO) data by the Sponsor, and safety analyses will not be performed using PRO data. However, if any PRO responses suggestive of a possible adverse event are identified during site review of the PRO data, the investigator will determine whether the criteria for an adverse event have been met and, if so, will report the event on the Adverse Event eCRF.

5.5 IMMEDIATE REPORTING REQUIREMENTS FROM INVESTIGATOR TO SPONSOR DURING PART 1 (OLE) AND PART 2 (SM)

Certain events require immediate reporting to allow the Sponsor to take appropriate measures to address potential new risks in a clinical trial. The investigator must report such events to the Sponsor immediately; under no circumstances should reporting take place more than 24 hours after the investigator learns of the event. See Section 5.5.2 for reporting requirements in Part 1 (OLE) and Part 2 (SM).

The following is a list of events that the investigator must report to the Sponsor within 24 hours after learning of the event, regardless of relationship to study drug:

- Serious adverse events (see Section 5.5.2 for more details)
- Adverse events of special interest (see Section 5.5.2 for more details)
- Pregnancies (see Section 5.5.3 for more details)

The investigator must report new significant follow-up information for these events to the Sponsor immediately (i.e., no more than 24 hours after becoming aware of the information). New significant information includes the following:

- New signs or symptoms or a change in the diagnosis
- Significant new diagnostic test results
- Change in causality based on new information
- Change in the event's outcome, including recovery
- Additional narrative information on the clinical course of the event

Investigators must also comply with local requirements for reporting serious adverse events to the local health authority and Institutional Review Board (IRB)/Ethics Committee (EC).

5.5.2 Reporting Requirements for Serious Adverse Events and Adverse Events of Special Interest

Part 1 (OLE)

For reports of serious adverse events and adverse events of special interest, investigators should record all case details that can be gathered immediately (i.e., within 24 hours after learning of the event) on the Adverse Event eCRF and submit the report via the electronic data capture (EDC) system. A report will be generated and sent to the Sponsor by the EDC system.

In the event that the EDC system is unavailable, a paper Clinical Trial Serious Adverse Event/Adverse Event of Special Interest Reporting Form and fax cover sheet should be completed and faxed to the Sponsor or its designee immediately (i.e., no more than 24 hours after learning of the event), with use of the fax numbers provided to investigators (see "Protocol Administrative and Contact Information & List of Investigators"). Once the EDC system is available, all information will need to be entered and submitted via the EDC system.

Part 2 (SM)

Reports of all PML-related serious adverse events and adverse events of special interest (regardless of relationship) should be entered into the Adverse Event eCRF. Events of related non-PML serious adverse events and pregnancies will be reported via faxing or by scanning and e-mailing the Serious Adverse Event/Adverse Event of Special Interest Reporting Form using the fax number or e-mail address provided to investigators.

5.5.3 Reporting Requirements for Pregnancies

5.5.3.1 Pregnancies in Female Patients

Part 1 (OLE)

Female patients of childbearing potential will be instructed to immediately inform the investigator if they become pregnant during the study or within 24 weeks after the last dose of study drug. A paper Clinical Trial Pregnancy Reporting Form should be completed and submitted to the Sponsor or its designee immediately (i.e., no more than 24 hours after learning of the pregnancy), either by faxing or by scanning and emailing the form using the fax number or email address provided to investigators. Pregnancy should not be recorded on the Adverse Event eCRF. The investigator should discontinue study drug and counsel the patient, discussing the risks of the pregnancy and the possible effects on the fetus. Monitoring of the patient should continue until conclusion of the pregnancy. Any serious adverse events associated with the pregnancy (e.g., an event in the fetus, an event in the mother during or after the pregnancy, or a congenital anomaly/birth defect in the child) should be reported on the Adverse Event eCRF.

In addition, the investigator will submit a paper Clinical Trial Pregnancy Reporting Form when updated information on the course and outcome of the pregnancy becomes available.

Part 2 (SM)

The same approach (e.g., immediate reporting) as described below applies; however, pregnancies should be reported directly to the Sponsor by completion of the Clinical Trial Pregnancy Reporting Form and either by faxing or by scanning and e-mailing the form using the fax number or e-mail address provided to investigators. Abortions or congenital anomalies/birth defects should be reported directly to the Sponsor with use of the Serious Adverse Event/Adverse Event of Special Interest Reporting Form as indicated in Section [5.5.2](#).

5.5.3.2 Pregnancies in Female Partners of Male Patients

Male patients will be instructed through the Informed Consent Form to immediately inform the investigator if their partner becomes pregnant during the study or within 24 weeks after the last dose of study drug. A paper Clinical Trial Pregnancy Reporting Form should be completed and submitted to the Sponsor or its designee immediately (i.e., no more than 24 hours after learning of the pregnancy), either by faxing or by scanning and emailing the form using the fax number or email address provided to investigators. Attempts should be made to collect and report details of the course and outcome of any pregnancy in the partner of a male patient exposed to study drug. When permitted by the site, the pregnant partner would need to sign an Authorization for Use and Disclosure of Pregnancy Health Information to allow for follow-up on her pregnancy. If the authorization has been signed, the investigator should submit a paper Clinical Trial Pregnancy Reporting Form when updated information on the course and outcome of the pregnancy becomes available. An investigator who is contacted by the male patient or his pregnant partner may provide information on the risks of the pregnancy and the possible effects on the fetus, to support an informed decision in cooperation with the treating physician and/or obstetrician.

5.5.3.3 Abortions

Any abortion should be classified as a serious adverse event (as the Sponsor considers abortions to be medically significant events), recorded on the Adverse Event eCRF, and reported to the Sponsor immediately (i.e., no more than 24 hours after learning of the event; see Section [5.5.2](#)).

5.5.3.4 Congenital Anomalies/Birth Defects

Any congenital anomaly/birth defect in a child born to a female patient or female partner of a male patient exposed to study drug should be classified as a serious adverse event, recorded on the Adverse Event eCRF, and reported to the Sponsor immediately (i.e., no more than 24 hours after learning of the event; see Section [5.5.2](#)).

5.5.4 Reporting Requirements for Prefilled Syringe Complaints/Events

The investigator should report all medical device complaints to the Sponsor. The investigator must document as much information as possible on the PD103 IMP Deviation Form, including product batch number and expiration date, and forward the complaint form to the Sponsor immediately (i.e., no more than 24 hours after the investigator becomes aware of the event). The PD103 IMP Deviation Form, together with pictures of the defective PFS, should be sent to [contact].

Where possible, the investigator will retrieve the PFS unit(s) involved in the complaint and attempt to return it to the Sponsor for further assessment, if necessary.

If the medical device complaint results in an adverse event, an Adverse Event eCRF must be completed and submitted through the EDC system. If the event is serious, the Adverse Event eCRF must be completed and submitted through the EDC immediately (i.e., no more than 24 hours after learning of the event), as outlined in Section 5.5.2. If the medical device complaint results in an adverse event to an individual other than the study patient, the device complaint must be reported on the PD103 IMP Deviation Form and the adverse event must be reported as a spontaneous adverse event to the Sponsor.

5.6 FOLLOW-UP OF PATIENTS AFTER ADVERSE EVENTS

5.6.1 Investigator Follow-Up

The investigator should follow each adverse event until the event has resolved to baseline grade or better, the event is assessed as stable by the investigator, the patient is lost to follow-up, or the patient withdraws consent. Every effort should be made to follow all serious adverse events considered to be related to study drug or study-related procedures until a final outcome can be reported.

During the study period, resolution of adverse events (with dates) should be documented on the Adverse Event eCRF and in the patient's medical record to facilitate source data verification.

All pregnancies reported during the study should be followed until pregnancy outcome.

5.6.2 Sponsor Follow-Up

For serious adverse events, non-serious adverse events of special interest, and pregnancies, the Sponsor or a designee may follow up by telephone, fax, electronic mail, and/or a monitoring visit to obtain additional case details and outcome information (e.g., from hospital discharge summaries, consultant reports, autopsy reports) in order to perform an independent medical assessment of the reported case.

5.7 POST-STUDY ADVERSE EVENTS

5.7.1 Post-Study Adverse Events Part 1 (OLE)

Patients Who Exit Part 1 (OLE) and Do Not Enter Part 2 (SM)

All patients should be encouraged to enter Part 2 (SM) of this study to allow for long-term PML monitoring and timely assessment of any symptoms that could be related to PML.

For those patients who do not enter Part 2 (SM) of this study, if investigators become aware of any serious adverse event after the end of the 12-week safety follow-up period that is believed to be related to prior study drug treatment, this should be reported to the Sponsor. In addition, the Sponsor should be notified if the investigator becomes aware of any post-study events of confirmed or suspected PML, regardless of relationship to study drug, for up to 2 years after the patient's last dose of study drug.

The investigator should report these events directly to Roche or its designee either by faxing or by scanning and e-mailing the paper Clinical Trial Serious Adverse Event/Adverse Event of Special Interest Reporting Form using the fax number or e-mail address provided to investigators.

Patients Who Exit Part 1 (OLE) and Enter Part 2 (SM)

Investigators should continue to provide follow-up data, if they receive it, to the Sponsor on unresolved adverse events.

5.7.2 Post-Study Adverse Events Part 2 (SM)

The Sponsor should be notified if the investigator becomes aware of any post-study serious adverse events that are believed to be related to prior study drug treatment.

For patients who withdraw from the study, the Sponsor should also be notified if the investigator becomes aware of any post-study events of confirmed or suspected PML, regardless of relationship to study drug, for up to 2 years after the patient's last dose of study drug.

The investigator should report these events directly to Roche or its designee either by faxing or by scanning and e-mailing the Serious Adverse Event/Adverse Event of Special Interest Reporting Form using the fax number or e-mail address provided to investigators.

5.8 EXPEDITED REPORTING TO HEALTH AUTHORITIES, INVESTIGATORS, INSTITUTIONAL REVIEW BOARDS, AND ETHICS COMMITTEES

The Sponsor will promptly evaluate all serious adverse events and adverse events of special interest against cumulative product experience to identify and expeditiously communicate possible new safety findings to investigators, IRBs, ECs, and applicable health authorities based on applicable legislation.

To determine reporting requirements for single adverse event cases, the Sponsor will assess the expectedness of these events for etrolizumab using the following reference document:

- Etrolizumab Investigator's Brochure

Within the Investigator's Brochure, the reference safety information is provided in Section 6.4 Identified Risks and Adverse Drug Reactions (Reference Safety Information).

The Sponsor will compare the severity of each event and the cumulative event frequency reported for the study with the severity and frequency reported in the applicable reference document.

Reporting requirements will also be based on the investigator's assessment of causality and seriousness, with allowance for upgrading by the Sponsor as needed.

All serious related (as assessed by the investigator and/or Sponsor) adverse events occurring in a patient administered etrolizumab at any time during the trial and assessed as unexpected per the reference safety information will be considered Suspected Unexpected Serious Adverse Reactions (SUSARs) for the purpose of regulatory reporting to all health authorities, with the exception of the U.S. Food and Drug Administration (FDA). For the FDA, SUSARs will be submitted as IND Safety Reports, in line with the FDA guidance "Safety Reporting Requirements for INDs and BA/BE Studies" dated December 2012.

The Sponsor will report all SUSARs into the EudraVigilance database in accordance with the "Detailed guidance on the collection, verification and presentation of adverse event/reaction reports arising from clinical trials on medicinal products for human use ('CT-3')."

To maintain the blind, investigators will be informed of all unexpected serious adverse events satisfying local regulatory reporting criteria but regardless of study drug assignment (i.e., they may also receive reports of patients on placebo).

6. STATISTICAL CONSIDERATIONS AND ANALYSIS PLAN

Because of the non-comparative character of the study, no statistical tests are planned; all efficacy parameters will be summarized descriptively. Efficacy in Part 1 (OLE) will be assessed across visits using absolute values and change from baseline for continuous outcomes, and dichotomous data (e.g., CDAI remission, clinical remission) will be evaluated using frequency counts and proportions. Demographic and baseline characteristics such as age, sex, race, region, use of corticosteroids and immunosuppressants, duration of disease, and CDAI, SF and AP scores will be summarized by use of descriptive statistics.

6.1 NUMBER OF PATIENTS

The maximum number of patients enrolled in the OLE-SM study is approximately 1150 (i.e., all patients enrolled in Study GA29144). No formal sample size calculations were performed.

6.2 SUMMARIES OF CONDUCT OF STUDY

The number of patients who enrolled in Part 1 (OLE) and Part 2 (SM) will be tabulated by country and study site. The number of patients who discontinued early (early discontinuation of OLE treatment or early termination from the study) or completed the study will be tabulated. Reasons for early discontinuation of treatment or early termination from the study will be listed and summarized. Any eligibility criteria exceptions and other major protocol deviations will also be summarized.

6.3 SAFETY ANALYSES FOR PART 1 (OLE)

The safety analyses will include all patients who received at least one dose of etrolizumab.

Safety will be assessed through descriptive summaries of adverse events, laboratory test results (serum chemistry, hematology including complete blood count with differential and platelet counts), and antibodies to etrolizumab.

6.3.1 Adverse Events

Verbatim descriptions of treatment-emergent adverse events will be coded and their incidence and observation time-adjusted rate will be summarized, as appropriate. A treatment-emergent adverse event is defined as any new adverse event reported or any worsening of an existing condition on or after the first dose of study drug. In addition, separate summaries will be generated for serious adverse events, deaths, and adverse events leading to discontinuation of etrolizumab.

Analyses will also be performed for:

- Systemic hypersensitivity events

Specific analyses will be performed for anaphylactic reactions using both the anaphylactic reaction MedDRA SMQ and Sampson's criteria (see [Appendix 10 Clinical Criteria for Diagnosing Anaphylaxis](#)).

- Serious infections, in particular GI infections
- Opportunistic infections
- Malignancies
- Injection-site reactions

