Appendix 9 Algorithm for the Evaluation of Progressive Multifocal Leukoencephalopathy

Appendix 10

Clinical Criteria for Diagnosing Anaphylaxis

These criteria are taken from a summary report from the second symposium on the definition and management of anaphylaxis, conducted by the National Institute of Allergy and Infectious Disease/Food Allergy and Anaphylaxis Network.¹ Anaphylaxis is highly likely when any one of the following three criteria is fulfilled:

1. Acute onset of an illness (minutes to several hours) with involvement of the skin, mucosal tissue, or both (e.g., generalized hives, pruritus or flushing, swollen lips-tongue-uvula)

AND AT LEAST ONE OF THE FOLLOWING:

- Respiratory compromise (e.g., dyspnea, wheeze-bronchospasm, stridor, reduced peak expiratory flow, hypoxemia)
 - Reduced blood pressure or associated symptoms of end-organ dysfunction (e.g., hypotonia, syncope, incontinence)
2. Two or more of the following that occur rapidly after exposure to a likely allergen for that patient (minutes to several hours):
 - Involvement of the skin-mucosal tissue (e.g., generalized hives, itch-flush, swollen lips-tongue-uvula)
 - Respiratory compromise (e.g., dyspnea, wheeze-bronchospasm, stridor, reduced peak expiratory flow, hypoxemia)
 - Reduced blood pressure or associated symptoms (e.g., hypotonia, syncope, incontinence)
 - Persistent gastrointestinal symptoms (e.g., crampy abdominal pain, vomiting)
 3. Reduced blood pressure after exposure to known allergen for that patient (minutes to several hours):
 - Infants and children: low systolic blood pressure (age specific)² or greater than 30% decrease in systolic blood pressure
 - Adults: systolic blood pressure of less than 90 mmHg or greater than 30% decrease from that person's baseline

¹ Sampson HA, Muñoz-Furlong A, Campbell RL, et al. Second symposium on the definition and management of anaphylaxis: summary report—second National Institute of Allergy and Infectious Disease/Food Allergy and Anaphylaxis Network symposium. *J Allergy Clin Immunol* 2006;117:391–7.

² Low systolic blood pressure for children is defined as less than 70 mmHg from 1 month to 1 year, less than (70 mmHg + [2 x age]) from 1 to 10 years, and less than 90 mmHg from 11 to 17 years.

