1. INTRODUCTION

The analyses described in this Statistical Analysis Plan (SAP) will supersede those specified in Protocol GA29145 for the purposes of reporting.

The purpose of this document is to describe the analyses for reporting out Part 1 of the Open-Label-Extension Safety Monitoring (OLE-SM) study for GA29145. This SAP will solely focus on reporting data collected during Part 1 (OLE) of GA29145.

This OLE-SM study is composed of two parts:

1. Part 1 is the OLE for eligible patients, during which etrolizumab, 105 mg SC, will be administered Q4W followed by a 12-week safety follow-up post-treatment.
2. Part 2 is the 92-week PML SM for all patients, during which no etrolizumab will be administered.

[figure not shown]
Patients who are enrolled in Part 1 (OLE) should participate in Part 2 (SM).

There may be patients from Study GA29144 who are ineligible for or choose not to participate in Part 1 (OLE) who will be asked to directly enroll in Part 2 (SM).

Key characteristics of the GA29145 OLE-SM are provided in [Table 1](#). Treatment arms and rollover of patients from induction/maintenance to GA29145 OLE-SM from parent CD studies are depicted in [Figure 1](#) and [Figure 2](#).

[figure not shown]
The maximum number of patients enrolled in GA29145 OLE-SM is approximately 1150 (i.e., all patients enrolled in Study GA29144). No formal sample size calculations were performed.

Figure 1 Study Schema for Part 1 (Open-Label Extension; OLE) of the OLE-SM Study

OLE=open-label extension; OLE-SM=open-label extension—safety monitoring; Q4W=every 4 weeks; Q12W=every 12 weeks; SC=subcutaneous.

Figure 2 Study Schema for Part 2 (Safety Monitoring; SM) of the OLE-SM Study

OLE=open-label extension; OLE-SM=open-label extension—safety monitoring; PML=progressive multifocal leukoencephalopathy; ~Q24W=approximately every 24 weeks.

Table 1 Key Characteristics of GA29145 OLE-SM in CD (Juniper)

Study	GA29145 (Phase III)	
Treatment (Number Exposed)	Open-label etrolizumab 105 mg SC Q4W (n= up to ~1150)	
Study Phases	OLE up to 10 years from FPI 12-week safety follow-up 92-week PML monitoring	
Key Eligibility Criteria	Part 1 (OLE)	Part 2 (SM)**

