4.2.2 Adverse Events

Verbatim descriptions of AEs will be mapped to the latest version of the Medical Dictionary for Regulatory Activities (MedDRA).

Adverse events (AEs) will include all terms recorded on the AE Case Report Form (CRF) pages (except pregnancies). For each recorded AE, the term entered by the investigator describing the event (the “reported term”) will be assigned a standardized term (the “preferred term”) and assigned to a superclass term on the basis of the Medical Dictionary for Regulatory Activities (MedDRA) World Health Organization (WHO) dictionary of terms. All analyses of AE data will be performed using the preferred terms and system organ class unless otherwise specified.

For the etrolizumab program, the adverse events of special interest (AESIs) are the following:

- Systemic hypersensitivity reactions and anaphylactic and anaphylactoid reaction which will be reported using the MedDRA anaphylactic reaction Standard MedDRA Query (SMQ) algorithmic and Hypersensitivity SMQ narrow.
- Neurological signs, symptoms, and AEs that may suggest possible progressive multifocal leukoencephalopathy (see Appendices 5 and 6 of Protocol)
- Suspected transmission of an infectious agent by the study drug
- Cases of potential drug-induced liver injury that include an elevated alanine aminotransferase (ALT) or aspartate aminotransferase (AST) in combination with either an elevated bilirubin or clinical jaundice, as defined by Hy’s Law

Specific AEs listed below will also be reported:

- Serious infections
- Gastrointestinal Infections
- Opportunistic infections
- Malignancies

- Injection site reactions

A listing or, summary table (e.g., n > 10) of all AEs suspected or confirmed, and AEs associated with COVID-19 will be generated. Associated AEs are defined as all AEs reported within a time window of 7 days prior and 30 days after the confirmed COVID-19 start date (dates inclusive). Additionally, a listing of patients experiencing 'long COVID-19' will be generated. This listing will include all AEs with a duration >30 days occurring after a confirmed COVID-19 infection or a positive PCR test.

All AESIs and specific AEs will be determined using a selection of eCRF tick box or MedDRA SMQs, Adverse Events Group Terms (AEGTs), High Level Term (HLTs), High Level Group Terms (HLGTs), System Organ Class (SOC), as appropriate.

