4.4 CHANGES TO PROTOCOL-PLANNED ANALYSES

The incidence of ATAs to etrolizumab was extensively evaluated in Ulcerative Colitis and Crohn's Disease within the phase 3 program, where no obvious impact on injection site reactions or other relevant safety parameters such as hypersensitivity was found. Following this evaluation, ATAs has been de-prioritised from a safety objective and outcome measure in GA29145 to an exploratory objective and outcome measure.

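### The protocol plans to analyse anaphylaxis by SMQ and by the Appendix 10 clinical criteria; the SAP plans SMQs only and does not list the omission as a change

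*Protocol*

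**What the plan says.** **Protocol.** Section 6.3.1 calls for specific analyses of anaphylactic reactions "using both the anaphylactic reaction MedDRA SMQ" and, alongside it, the clinical criteria set out in Appendix 10. That appendix opens its list with "Anaphylaxis is highly likely when any one of the following three criteria is fulfilled". The three criteria turn on speed of onset, skin or mucosal involvement, respiratory compromise, gastrointestinal symptoms and blood pressure. For adults the blood-pressure element is a systolic value under 90 mmHg or a fall of more than 30% from the patient's own baseline. Protocol 5.1.1.2 and 5.3.3 also refer investigators to Appendix 10 when they deal with these events as adverse events of special interest (AESIs).

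**SAP.** The line in 4.2.2 that deals with systemic hypersensitivity, anaphylactic and anaphylactoid reactions says they "will be reported using the MedDRA anaphylactic reaction Standard MedDRA Query (SMQ) algorithmic and Hypersensitivity SMQ narrow". Later in the same section a general sentence covers every AESI: "All AESIs and specific AEs will be determined using a selection of eCRF tick box or MedDRA SMQs", or other MedDRA groupings, as appropriate. Neither sentence mentions Appendix 10 or its criteria.

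**Precedence and declared changes.** SAP section 1 says that its analyses "will supersede those specified in Protocol GA29145 for the purposes of reporting", and refers the reader to 4.4 for changes to the protocol-planned analyses. Section 4.4 records one change: "ATAs has been de-prioritised from a safety objective and outcome measure in GA29145 to an exploratory objective" and outcome measure. Section 5 says there is no supporting document.

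**The concern.** The incidence and severity of hypersensitivity reactions is a safety objective (SAP 1.1) and a safety outcome measure (SAP 1.3.2), and SAP section 4 promises that all safety outcome measures will be reported. Anaphylaxis is the most serious component of that outcome. The protocol chose to examine it in two ways, one through coded terms and one through the clinical features of the case. If the SAP is followed as written, the second is not done.

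Two features of the study make this worth correcting. Patients who received placebo in GA29144 may have their first etrolizumab exposure here, which is the protocol's own reason for giving the first four injections in clinic (5.1.1.2). In addition, SAP 4.4 downgrades the antibody analysis partly because no obvious impact on hypersensitivity was found elsewhere in the programme, and SAP 1.3.3 keeps antibody incidence out of the primary CSR. The hypersensitivity analysis should therefore follow the plan or openly say where it departs from it.

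**Working it through.** The point rests on comparing texts. The study is descriptive, with no hypotheses or tests (SAP 2.1), and the plan gives no figure to reproduce.

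**1. Methods planned for anaphylaxis**

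| | Coded-term methods | Clinical-criteria methods |
|---|---|---|
| Protocol 6.3.1 | 1 (anaphylactic reaction SMQ) | 1 (Appendix 10) |
| SAP 4.2.2 | 2 (anaphylactic reaction SMQ, algorithmic; Hypersensitivity SMQ, narrow) | 0 |

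The SAP adds a coded-term search that protocol 6.3.1 does not name and omits the clinical classification that it does name.

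**2. Does the protocol sentence survive by default?** Not clearly. SAP section 1 gives the SAP precedence for reporting, and 4.2.2 deals with anaphylaxis explicitly, so its silence on Appendix 10 reads as removal.

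**3. Is the removal declared?** No. Section 4.4 lists one change (antibodies) and none concerning anaphylaxis. Section 5 rules out a companion document that might restore the analysis.

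**4. Could it be an oversight?** Possibly; this is inference. The AESI list in SAP 4.2.2 is introduced as belonging to the etrolizumab programme, and for PML it cites protocol Appendices 5 and 6. In this protocol those are the CDAI and the abdominal pain questionnaire; the PML worksheet and algorithm are Appendices 8 and 9. The list may have been carried over without being matched to this protocol.

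**5. What one case is worth.** Protocol 5.1.1.2 reports one serious hypersensitivity event and no anaphylaxis in the completed Phase I/II trials, so counts near zero are plausible. The smallest step in a crude incidence is 1/N:

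- N = 1150, the maximum enrolment: 1/1150 = 0.00087, or 0.09%.
- N = 500 dosed in Part 1, an assumption for illustration: 1/500 = 0.002, or 0.2%.

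The first figure is a floor. The 1150 covers all GA29144 patients, including those who go straight to Part 2, whereas the analysis set (SAP Table 3) is patients dosed in Part 1. Neither figure says how often the two methods would disagree, and the documents contain nothing from which to derive that.

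**6. Can the criteria be applied to existing data?** In part. Systemic hypersensitivity and anaphylactic events go to the Sponsor within 24 hours (protocol 4.2.2, 5.1.1.2, 5.3.3), so case details should exist. Criteria 1 and 2 can be met without a blood-pressure reading, for example by rapid-onset skin and respiratory signs. Criterion 3 cannot. Routine vital signs are taken before dosing, at clinic visits only (protocol 4.4.4.2), and doses after the fourth are usually given at home (protocol 4.2.2). Some cases will therefore lack the data needed to rule anaphylaxis in or out.

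**The case against.** The strongest reply is that this is a documentation mismatch with little consequence. A reader might infer from the SMQ line that anaphylaxis now rests on coded terms alone, or that it has lost its clinical definition. The documents do not support either reading. The general sentence in SAP 4.2.2 allows an eCRF tick box for AESIs, and investigators are referred to Appendix 10 for these events, so clinical judgement enters at reporting. Protocol 5.4.6.2 asks for a known diagnosis to be recorded in place of its separate symptoms. Severity is graded by NCI CTCAE whatever the SMQ returns. A case of anaphylaxis should also appear among adverse events leading to discontinuation, given protocol 4.5.2. The Sponsor may seek case details for its own medical assessment (protocol 5.6.2).

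It is equally tempting to argue that the SMQ algorithm will flag unrelated coincident terms or miss true cases. Neither document describes the algorithm, so that argument is not used here.

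The reply also notes that the SAP may lawfully narrow the protocol's methods for a synoptic report, and that no decision rule depends on the count.

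All of this limits the size of the point, but it does not remove it. The line specific to anaphylaxis names only SMQs. A tick box filled in by an investigator is not a planned classification of cases against Appendix 10. A SAP that narrows a safety analysis should say so in the section it reserves for that purpose, and 4.4 does not.

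**Conclusion.** The point holds in a limited form. The SAP omits a clinical-criteria analysis of anaphylaxis that protocol 6.3.1 pre-specifies, and does not list the omission in 4.4. This is more than a missing detail, because an explicit commitment on the most serious part of a named safety outcome has lapsed. It does not undermine the safety evaluation as a whole.

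The effect on the anaphylaxis count cannot be quantified from the documents. What can be said is conditional: if events are as rare as the Phase I/II experience suggests, a single reclassified case could move the report from no anaphylaxis to some, or the reverse. The conclusion assumes that the SAP is followed as written and that no separate case-review plan exists, which SAP section 5 supports.

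**What to change.** Add to SAP 4.2.2, in substance: events flagged by the anaphylactic reaction SMQ (algorithmic), or reported as systemic hypersensitivity, anaphylactic or anaphylactoid AESIs, will also be classified by Sponsor medical review of the existing case data against protocol Appendix 10 as met, not met or not classifiable. The SMQ count and the Appendix 10 count will both be presented, with the dosed OLE population as denominator.

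This scope leaves out events flagged only by the narrow Hypersensitivity SMQ, which keeps the review close to cases already reported to the Sponsor. The third category is needed because post-dose blood pressure is not routinely recorded, especially after home dosing.

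The cost is medical review of what is probably a small number of cases, some of which may prove unclassifiable. No new data collection or change to patient care is involved. If the analysis was dropped deliberately, one sentence in SAP 4.4 stating that and giving the reason would settle the matter.
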